### 8.4 Treatment Compliance and Exposure

Treatment compliance (see [Section 5.6](#)) will be summarized for each treatment group by means of descriptive statistics (n, mean, SD, median, Q1, minimum, Q3, and maximum) and/or frequency tables (compliance < or ≥80%).

The total number of days of patch application during the whole study will be presented overall and by treatment group. Besides, the exposure duration by subject will be summarized, quantitatively and by category, overall and by treatment group. Exposure duration will be calculated regardless of temporary interruptions, as follows:

$\text{Date of last patch application} - \text{Date of first patch application} + 1$
--

The total dose of peanut protein received during the study (mg) will also be summarized overall and by treatment group.

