## 3 INVESTIGATIONAL PLAN

### 3.1 Overall Study Design and Plan

This is a 12-month, Phase III, double-blind, placebo-controlled, randomized study to assess the efficacy and safety of Viaskin® Peanut, dosed at 250 µg peanut protein (per patch) in peanut-allergic children from 4 through 11 years of age.

The overall maximum study duration for each subject is approximately 61 weeks (6-week screening period, 12-month treatment period and 2-week follow-up period).

During the maximum 6-week screening period, subjects will undergo a first screening visit and an entry double-blind, placebo-controlled food challenge (DBPCFC) to peanut to confirm their allergy and their entry peanut eliciting dose (ED). The starting dose of the challenge will be 1 mg peanut protein and will escalate up to a highest dose of 300 mg peanut protein. Subjects who react at or below the dose of 300 mg peanut protein are considered eligible. Randomization of eligible subjects will occur in a 2:1 ratio to Viaskin® Peanut dosed at 250 µg peanut protein (active treatment) or placebo. Subjects will be stratified at randomization by their entry/screening DBPCFC ED in one of the following two strata:

---

 PEPITES: A Double-blind, Placebo-controlled, Randomized Phase III Pivotal Trial to Assess the Efficacy and Safety of Peanut Epicutaneous Immunotherapy with Viaskin® Peanut in Peanut-allergic Children

- Stratum 1: children with a screening ED of 1 mg, 3 mg or 10 mg;
- Stratum 2: children with a screening ED of 30 mg, 100 mg or 300 mg.

The randomization scheme will ensure that the ratio of active treatment to placebo is maintained in each stratum.

Subjects randomized in the study and consenting for the genetic analysis on a voluntary basis will be assessed for mutations in the filaggrin gene. Subjects' participation for this genetic analysis will be optional.

Subjects will apply a Viaskin® patch containing either peanut protein or placebo daily for a period of 12 months. At Month 12, a second DBPCFC to peanut will be performed, with a starting dose of 1 mg peanut protein with escalation up to a highest dose of 2,000 mg peanut protein. This evaluation will help determine the primary efficacy endpoint of this pivotal study.

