#### 4.7 Study duration, treatment exposure and compliance

The overall study duration for each subject will be approximately 61 weeks (6-week screening period, 12-month treatment period and 2-week follow-up period).

Study duration (days) will be calculated as:

- Last study visit date - Date of informed consent +1.

During the 12-month blinded treatment period, the Viaskin® patch must be applied on the skin for 24 hours every day, except during the initiation of treatment, where the duration of application of the Viaskin® patch will be progressively increased as follows:

- During the first week (from Day 1 through Day 7), the patches will be applied for 6 hours every day,
- During the second week (from Day 8 through Day 14), the patches will be applied for 12 hours every day,
- From the third week onwards (Day 15), the patches will be applied for the entire 24 hours daily.

Treatment exposure will be based on:

- The exposure duration (in days, regardless of treatment interruption), calculated for the following periods:
  - ⌞ Over the whole study period as: Date of last patch application – Date of first patch application +1,
  - ⌞ At each study visit (Day 8, Month 1, 3, 6, 9, 12) as: Date of last patch application before the visit – Date of first patch application at the preceding visit+1.
- The total dose of peanut protein (in mg) received via the patch during the study, calculated for the following periods:
  - ⌞ Over the whole study period as: Exposure duration (in days) \* Actual treatment dosage,
  - ⌞ At each study visits, as: Exposure duration at the visit (in days) \* Actual treatment dosage.

The compliance (%) determined for the following periods:

- Over the whole study period as:

$$100 \left( \frac{\text{Number of patches dispensed} - \text{Number of patches returned}}{\text{Exposure duration in days}} \right)$$

- At each study visit (Day 8, Month 1, 3, 6, 9, 12) as:

$$100 \left( \frac{\text{Nb of patches dispensed}(\text{visit } n - 1) - \text{Nb of patches returned}(\text{visit } n)}{\text{Date of } (\text{visit } n) - \text{Date of } (\text{visit } n - 1)(1)} \right)$$

 Date of current visit – Date of previous visit+1 for Day 8

Compliances exceeding 100% will be set to 100%.

Global compliance of at least 80% over the treatment period is sought.

Additionally, the average daily application duration (in hours) will be summarized descriptively using the subject diary data for the following periods:

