- r D1 to D7,
- r D8 to D14,
- r D15 to M3 (D90),
- r M3 (D91) to M6 (D185),
- r M6 (D186) to M9 (D275),
- r M9 (D276) to M12 (end of treatment),
- r D15 to M12

If more than one patch is applied the same day, the daily duration considered is the cumulative application duration of these patches.

In case patches are sequentially applied on the same day: if the end date/time of first patch is not documented, the application date/time of the next patch will be used for imputation.

The percentage of days with no patch application, per subject diary reported data, will also be tabulated, overall and for each of the above periods.

A patch will be considered as “applied” if the date and time of application is documented in the diary.

The start and/or end date/time of patch application used to calculate the duration of patch application are extracted from the diary.

Inconsistencies in the diaries are not queried and only self-evident corrections according to the Data Validation specifications will be made; therefore, inconsistent date/time of patch application or patch removal may remain in the data. In case where calculation of patch application duration leads to a negative value or duration cannot be calculated (missing date or time of removal or invalid dates or times) then:

CCI

CONFIDENTIAL

Project Document Version No. 3.0

Project Document Effective Date: 04-Oct-2017

Page 31 of 79

- The duration of patch application will be considered as ‘unknown’ and not used in the calculation of the average duration of patch application
- For any other calculation based on the number of days with patch application, this day will be considered as a day with application.

These data will be reported as:

- Descriptive statistics for study duration, treatment exposure duration, total dose of protein and compliance (overall and by visit - except for study duration -),
- Number and percent per category of overall exposure (in days, categories are: 1-7, 8-14, 15-30, 31-90, 91-185, 186-275, 276-365, >365), compliance in classes (<80%, ≥80%).

Study duration, treatment exposure and compliance will be summarized for the Safety population in tables that will be produced for each treatment group and overall (except for peanut protein dose that will only be described for the Viaskin Peanut 250 µg arm), globally and by screening ED subgroup.

All data including documentation of treatment interruptions will be listed by treatment group.

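### SAP 4.7 counts days without a patch as dose received, so the active arm's total peanut protein is too high for children with net missed patch days

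*SAP*

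**What the plan says.** SAP 4.7 builds the dose summary in two steps. The first is duration: "The exposure duration (in days, regardless of treatment interruption), calculated for the following periods". For the whole study it is computed thus: "Over the whole study period as: Date of last patch application – Date of first patch application +1". The second is dose, introduced as "The total dose of peanut protein (in mg) received via the patch during the study, calculated for the following periods" and computed as "Exposure duration (in days) \* Actual treatment dosage". The same product is used for each visit interval, with that interval's exposure duration. The dose per patch is fixed: the product is "dosed at 250 µg peanut protein (per patch) in peanut-allergic children from 4 through 11 years of age", and one patch is applied per day. The section limits the dose description to the active arm.

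The same section holds two sources on patches actually used, and neither enters the dose. Compliance is the number of patches dispensed minus the number returned, over exposure duration. From the diary, "The percentage of days with no patch application, per subject diary reported data, will also be tabulated".

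Protocol 8.4 treats days of patch application, exposure duration and total dose as separate items. It tells the analyst to ignore temporary interruptions for exposure duration only. For dose it gives no formula: "The total dose of peanut protein received during the study (mg) will also be summarized overall and by treatment group". The list of changes from the protocol in SAP 4.13 does not mention the dose calculation.

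**The concern.** The row is labelled as dose received, but the formula gives the dose scheduled between two dates. Since dosage is constant, the row is exposure duration multiplied by 0.25 and carries no further information. A child who misses a fifth of the patches and one who misses none get the same total if their first and last patch dates match.

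Missed days are foreseen. Protocol 5.2.2 has families stop patching during chicken pox, measles or active eczema on the back. Protocol 6.2.1.3.5 has a transient stop for vesicles or ulcerative lesions. Protocol 4.3.1 refers to treatment interruptions for severe rash or dermatitis. At stake is the accuracy of one line in the exposure table of a pivotal trial, the line a reader would use to relate dose received to safety or response.

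**Working it through.** The documents state no total dose in mg, so there is no figure to reproduce. The check compares the SAP formula with a patch-based dose.

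**Inputs**
- Dose per patch: 250 µg = 0.25 mg, one patch per day (SAP 3.1, Protocol 5.2).
- Exposure duration: last patch date minus first patch date plus 1 (SAP 4.7).
- Patches used: dispensed minus returned, the compliance numerator (SAP 4.7).
- Compliance levels: 80% is the target in SAP 4.7; 90% and 95% are illustrations.
- Span from first to last patch: 365 days, an assumption for 12 months. The documents do not fix it, because visit windows and early stopping move it.
- Dosage term in the formula: read as 250 µg per day. The SAP does not define it further.

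**Formulas**
- SAP dose = span × 0.25 mg.
- Patch-based dose = span × compliance × 0.25 mg.
- Excess = missed days × 0.25 mg, or 1/compliance − 1 relative to the patch-based dose.

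**Results, 365-day span.** SAP dose = 365 × 0.25 = 91.25 mg in every row.

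| Compliance | Patch-based dose | Excess | Relative excess |
|---|---|---|---|
| 100% | 91.25 mg | 0 | 0% |
| 95% | 91.25 × 0.95 = 86.7 mg | 4.6 mg | 1/0.95 − 1 = 5% |
| 90% | 91.25 × 0.90 = 82.1 mg | 9.1 mg | 1/0.90 − 1 = 11% |
| 80% | 91.25 × 0.80 = 73.0 mg | 18.25 mg | 1/0.80 − 1 = 25% |

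**Single interruption.** Fourteen days without a patch add 14 × 0.25 = 3.5 mg, and 365/351 − 1 = 4.0%.

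**Sensitivity to the span.** With 360 days and 80% compliance, 360 × 0.25 = 90.0 mg against 72.0 mg, again 25%. The relative excess depends only on compliance.

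**Replacement patches.** Protocol 5.2 allows a same-day replacement when a patch comes off within 2 hours. In a pure patch count, 10 missed and 5 replaced leave an excess of 5 × 0.25 = 1.25 mg; 10 missed and 10 replaced leave none; 5 missed and 10 replaced put the SAP figure 1.25 mg below the count. Counting diary days with a patch avoids this offset.

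**The case against.** The strongest reply is that little depends on this row and the missing information is printed beside it. Total dose is a descriptive summary. It enters neither the testing hierarchy in SAP Table 2 nor any analysis-set rule; per-protocol exclusion uses compliance. SAP 4.7 also reports compliance, average daily hours worn, percentage of days without a patch, and a listing of interruptions. Because overall compliance has exposure duration as its denominator, the SAP dose times compliance gives the patch-count dose for any child whose compliance was not capped at 100%. All of this stands and limits the weight of the point. It does not make the label true.

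The size is also fairly contested. The 25% belongs to a child at the compliance target, not to a typical child. Protocol 1.3 describes very good compliance in earlier studies, and at 95% the excess is about 5%. That stands too.

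A reader might infer more than the documents support:
- **That exposure in general is overstated.** Both documents openly define exposure duration as ignoring interruptions, so it is not wrong by its own definition. Only total dose is affected.
- **That every child is affected.** Dose is described for the active arm only, days after the last patch are not counted, and replacements can offset missed days in a patch count.
- **That every child would show 91.25 mg.** That holds only for a 365-day span.
- **That the excess is greatest in children with severe local reactions.** Protocol 5.2.1 has the patch removed and the next one applied the next day, so these children mainly lose hours rather than patch days. The documents do not quantify missed days in this group.
- **That the true dose is available.** Dispensed minus returned does not show that a patch was worn. Diary inconsistencies are not queried, and a day whose wear time cannot be computed counts as a day with application. Neither source reflects the 6-hour and 12-hour weeks or early removals.

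**Conclusion.** The point holds for one quantity: the active arm's total peanut protein, overall and per visit interval. As written, the formula reports as received some protein that was never applied, for each active-arm child with net missed patch days between first and last patch. The relative excess is 1/compliance − 1, ranging from about 5% at 95% compliance to 25% at 80%, and zero when no patches are missed.

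This rests on reading the dosage term as a constant 250 µg per day. If it meant an average over patches actually applied, the excess would disappear, but nothing in the SAP supports that reading. The mg figures also assume a 365-day span.

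The protocol does not require this formula, since it ties the interruption rule to duration alone. The correction is worth making because a reported number is wrong as labelled. Its consequence is limited to that descriptive summary; no efficacy conclusion depends on it.

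**What to change.** In SAP 4.7, define total dose, for the whole study and for each visit interval, as the number of diary days with a patch applied × 0.25 mg. Patches dispensed minus returned × 0.25 mg is an acceptable alternative; name the one chosen. Add a note that the result approximates patches applied and does not account for hours worn. Keep exposure duration as its own line, unchanged. Record the change in SAP 4.13.

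If the present formula is kept, relabel the row as planned dose over the exposure period, so that it is not read as dose received.

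The cost is one formula or one label, plus reprogramming of one summary. No new data are needed: patch counts already feed compliance, and SAP 4.7 already defines when a diary patch counts as applied.

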## 4.8 Efficacy Evaluation

### 4.8.1 Analysis and Data Conventions

The primary efficacy endpoint in this study is the difference between percentage of treatment responders in the active Viaskin® Peanut 250 µg group compared to the placebo group after 12 months of EPIT treatment.

#### 4.8.1.1 Multi-center Studies

Considering the expected small number of subjects to be randomized by center, the center effect will not be investigated. Nevertheless, the region (Australia/ Europe/ North America) effect will be investigated on the ITT population for the primary efficacy endpoint.

#### 4.8.1.2 Handling of Dropouts or Missing Data

##### Primary and Secondary Analyses

Analyses of the efficacy endpoints (primary and secondary) will be based on the ITT population. In the event of missing data imputation rules will be incorporated in respective analytical details.

##### Cumulative Reactive Dose (CRD)

The cumulative reactive dose of peanut (CRD) will be calculated as follow

CCI

CONFIDENTIAL

Project Document Version No. 3.0

Project Document Effective Date: 04-Oct-2017

Page 32 of 79

- If the ED reported by the investigator in the eCRF is missing, then the CRD is missing
- If the ED reported by the investigator in the eCRF is not missing then the CRD is calculated as the sum of all doses given, including also the repeated and partial doses; doses greater than the ED are not included in the calculation. Example:  
For a particular patient if the set of recorded doses is {1, 3, 10, 30, 100, 300, 300, 1000}, and recorded ED = 300mg, then  $CRD = 1 + 3 + 10 + 30 + 100 + 2 \times 300 = 744mg$ .

No imputation will be performed for other efficacy, safety and exploratory parameters. In those instances observed data will be used, excepted for safety data where partial or missing data will be imputed according to the most conservative approach (See [Section 4.9.1: Adverse Events](#)).

Actual values will be presented in listings.

#### 4.8.1.3 Multiple Comparisons/Multiplicity

In order to handle the multiple comparisons versus placebo, the overall type-I error will be controlled at a level of 5% (2-sided) by the use of a hierarchical inferential approach. The primary analysis in the overall population must be positive according to the clinical relevance criterion (described in [section 4.8.2](#)) before drawing inferential conclusions about the secondary comparisons as defined by the hierarchical order. The first secondary efficacy analysis (difference in treatment response in Screening ED subgroup 2) must meet its success criterion before drawing an inferential conclusion about the next secondary comparison (difference in treatment response in Screening ED subgroup 1). Inferential conclusions about the next successive secondary comparisons require meeting the success criterion of the previous comparison. The pre-defined hierarchical order and success criteria are summarized in [Table 2](#).

**Table 2: Pre-defined Hierarchical Order for Analysis of Efficacy Endpoints**

Order	Efficacy endpoints (at M12)	Population or sub-group	Success criterion	Method / SAS® Procedure
1	Difference in percentages of treatment responders	ITT Overall	95% CI lower bound $\geq 15\%$	2-sided Newcombe 95% CI (SAS® FREQ procedure with RISKDIFF option)
2	Difference in percentages of treatment responders	ITT Screening ED subgroup 2	95% CI lower bound $>0\%$	2-sided Newcombe 95% CI (SAS® FREQ procedure with RISKDIFF option)
3	Difference in percentages of treatment responders	ITT Screening ED subgroup 1	95% CI lower bound $>0\%$	2-sided Newcombe 95% CI (SAS® FREQ procedure with RISKDIFF option)
4	Cumulative reactive dose	ITT Overall	$p \leq 0.05$	ANCOVA
5	Peanut protein ED	ITT Overall	$p \leq 0.05$	ANCOVA
6	Difference in percentages of treatment responders	ITT Age group 6-11 years of age	95% CI lower bound $>0\%$	2-sided Newcombe 95% CI (SAS® FREQ procedure with RISKDIFF option)
7	Difference in percentages of treatment responders	ITT Age group 4-5 years of age	95% CI lower bound $>0\%$	2-sided Newcombe 95% CI (SAS® FREQ procedure with RISKDIFF option)
8	Difference in percentage of subjects responsive to a cumulative dose $\geq 1,444$ mg peanut protein	ITT Overall	95% CI lower bound $>0\%$	2-sided Newcombe 95% CI (SAS® FREQ procedure with RISKDIFF option)
9	Difference in percentage of subjects unresponsive to a cumulative dose $\geq 1,444$ mg peanut protein	ITT Overall	95% CI lower bound $>0\%$	2-sided Newcombe 95% CI (SAS® FREQ procedure with RISKDIFF option)
10	Cumulative reactive dose	ITT Screening ED subgroup 2	$p \leq 0.05$	ANCOVA

CCI

CONFIDENTIAL

Project Document Version No. 3.0

Project Document Effective Date: 04-Oct-2017

Page 34 of 79

Order	Efficacy endpoints (at M12)	Population or sub-group	Success criterion	Method / SAS® Procedure
11	Peanut protein ED	ITT Screening ED subgroup 2	$p \leq 0.05$	ANCOVA
12	Cumulative reactive dose	ITT Screening ED subgroup 1	$p \leq 0.05$	ANCOVA
13	Peanut protein ED	ITT Screening ED subgroup 1	$p \leq 0.05$	ANCOVA
14	Difference in percentage of subjects passing the challenge (percentage of subjects unresponsive to the highest dose of peanut protein)	ITT Overall	95% CI lower bound $>0\%$	2-sided Newcombe 95% CI (SAS® FREQ procedure with RISKDIFF option)

Abbreviations: CI = Confidence Interval; p = p-value; ANCOVA = Analysis of covariance; ED = Eliciting dose; ITT = Intent-to-treat.

#### 4.8.1.4 Interim Analyses

No interim analyses are planned. Hence no adjustments for multiplicity are required.

#### 4.8.1.5 Examination of Subgroups

The treatment effect for the primary efficacy variable will be examined as secondary efficacy analyses in each of the subgroup defined according to the screening ED. Sample size has been calculated to demonstrate a treatment difference at the level of 5% in each of the screening ED stratum based on a lower bound of the 2-sided Newcombe 95% CI of the difference between active treatment and placebo response rates  $>0\%$ :

- At a power of 99% in stratum 1, with an expected response rate of 60% in the active treatment vs. 10% for placebo, both estimated using missing=failure method
- At a power of 95% in stratum 2, with an expected response rate of 30% in the active treatment vs. 10% for placebo, both estimated using missing=failure method.

To handle cases of randomization stratum error (i.e. the stratum recorded in the IWRS was not consistent with the actual screening ED value), screening ED subgroups were considered for secondary analyses using the actual screening ED value (i.e. subjects will be considered in the screening ED subgroup corresponding to the actual screening ED value).

The treatment effect for the primary efficacy variable will also be examined as secondary

CCI

CONFIDENTIAL

Project Document Version No. 3.0

Project Document Effective Date: 04-Oct-2017

Page 35 of 79

efficacy analyses in each of the following age groups: 4-5 year of age, 6-11 year of age (respectively [4-6[, [6-12[).

Response rates by treatment groups and treatment effect will also be provided descriptively, as exploratory analysis, for each region and on the following subgroups:

- Gender (Male/Female)
- Race (White/Black or African American/Asian/Other)
- Subjects with / without history of asthma
- Subjects with / without history of allergy other than peanut
- Subjects with / without history of atopic dermatitis or eczema.

Analysis will be performed only on subgroups containing at least 15 subjects.

According to the sample size of each subgroup (if  $N < 50$ ), exact 2-sided 95% CIs will be provided instead of 2-sided Newcombe 95% CIs for the difference in response rates. In the presence of sparse data (i.e. at least one of the percentages is zero) the following will not be presented:

- within-treatment confidence intervals around response rate (of 0%),
- between-treatment comparative p-value.

A forest plot will be provided summarizing the primary efficacy variable in the above subgroups.

No other subgroup analysis will be performed.

